6.4. Post-treatment Assessments

6.4.1. Early Termination Visit Assessments

6.4.1.1. Early Termination Visit Assessments - Treatment Group 1 and 2

6.4.1.1.1. Early Termination visit after Day 1 and prior to Day 15

If a participant discontinues oral GS-6207 or decides not to initiate SC GS-6207 at Day 15, an Early Termination Visit should be performed within 72 hours of the decision to discontinue the study drug. Participants will be asked to continue to attend study visits until completion of the Day 15 visit. Participants will be required to complete 90-Day Follow up Visit. Refer to Section 6.4.2

6.4.1.1.2. Early Termination visit after Day 15 and prior to Week 80

If a participant decides to discontinue GS-6207 (SC and oral) prior to Week 80, an Early Termination Visit should be performed within 72 hours of decision to discontinue study drug.

The participant will be asked to continue attending the scheduled study visits through the Week 80 visit.

- If the participant decides to discontinue SC GS-6207 but continues to attend study visits through Week 80, no follow up visits are required.
- If the participant decides to discontinue SC GS-6207 and does not continue to attend study visits through Week 80, the 30-Day, 90-Day and 180-Day Follow Up Visits are required. Refer to Section 6.4.2. The 180-Day follow up may be conducted via a phone call per the investigator's discretion.
- If a participant discontinues oral GS-6207 during the Oral Bridging Period and does not continue to attend study visits through their next SC dosing visit, the participant will be required to complete the 90-Day Follow up-Visit (see Section 6.4.2).

6.4.1.1.3. Early Termination visit after Week 80

If a participant continues the study after completing the Week 80 visit, but discontinues GS-6207 (SC and oral) prior to study completion, an Early Termination Visit should be performed within 72 hours of decision to discontinue study drug.

- If the participant decides to discontinue SC GS-6207 but continues to attend the scheduled study visits through their next SC dosing visit, they will complete all assessments except SC dosing at the last visit and complete the study. No further follow up visits are required.

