- If the participant decides to discontinue SC GS-6207 and does not continue to attend the scheduled study visits through their next SC dosing visit, the 30-Day, 90-Day and 180-Day Follow Up Visits are required. Refer to Section 6.4.2. The 180-Day Follow Up may be conducted via a phone call per the investigator's discretion.
- If a participant discontinues oral GS-6207 during the Oral Bridging Period and does not continue to attend study visits through their next SC dosing visit, the participant will be required to complete the 90-Day Follow up Visit (see Section 6.4.2).

6.4.1.2. Early Termination Visit Assessments - Treatment Group 3

If the participant discontinues their study regimen prior to Week 64 visit, the participant will be asked to return to the clinic within 72 hours of stopping study treatment for an Early Termination visit. The participant will be asked to continue to attend study visits through Week 80.

- If the participant agrees to continue to attend study visits through Week 80, no follow up visits are required.
- If the participant does not agree to continue to attend study visits through Week 80, the 30-Day and 90-Day Follow Up Visits are required. Refer to Section 6.4.2

If a participant discontinues the study drug between Week 64 and Week 80 OR after completing the Week 80 visit but prior to study completion, the Early Termination visit should be performed. The participant will complete the 30-Day and 90-Day follow-up visits after completion of the Early Termination visit.

6.4.1.3. Early Termination Visit Assessments - Treatment Group 4

If the participant discontinues their study regimen prior to Week 64 visit, the participant will be asked to return to the clinic within 72 hours of stopping study drug for an Early Termination visit. The participant will be asked to continue to attend study visits through Week 80.

- If the participant agrees to continue to attend study visits through Week 80, no follow up visits are required.

- If the participant does not agree to continue to attend study visits through Week 80, the 30-Day Follow Up Visit is required. Refer to Section 6.4.2

If a participant discontinues the study drug between Week 64 and Week 80, the Early Termination visit should be performed. The participant will complete the 30-Day Follow-Up visit after completion of the Early Termination visit.

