3.8. Analysis Visit Windows

3.8.1. Definition of Key Dates and Study Day

Study Day 1 is defined as the day when the first dose of study drug was taken, as recorded on the Study Drug Administration eCRF. For subjects in Treatment Groups 1-3, the earliest of the first dose dates of any component (ie, LEN or F/TAF) is considered as the first dose date of the study drug.

Last Dose Date is defined as follows for subjects who prematurely discontinued study drug according to Study Drug Completion eCRF.

- For subjects who receive SC injection, the last dose date is defined as the latest nonmissing end date of the study drug used with LEN.
- For subjects who do not receive SC injection, the last dose date is defined as the earliest of the last dose date of any study drug.
- If the date of last dose is incomplete or missing (eg, due to lost to follow-up), the latest nonmissing study drug start dates and end dates, the clinic visit dates, and the laboratory visit dates excluding the dates of any follow-up visits will be used to impute the last dose date.

Study Days are calculated relative to Study Day 1 of study drug and derived as follows:

- For postdose study days: Assessment Date – First Dose Date + 1
- For days prior to the first dose: Assessment Date – First Dose Date

Baseline Value is defined as the last value obtained on or prior to the first dose of study drug.

Last Study Date is the latest nonmissing clinic visit dates, and/or the laboratory visit dates, and/or latest AE onset date and end date, whichever is latest, including the any follow-up visit dates, for subjects who prematurely discontinued study according to the Study Completion eCRF.

Last Exposure Date is defined as follows for subjects who prematurely discontinued study drug according to Study Drug Completion eCRF. This date is defined considering the prolonged exposure of LEN after the last dose date of LEN.

- Treatment Groups 1 and 2:
 - For subjects who receive SC injection, last exposure date is defined as last study date.
 - For subjects who do not receive SC injection, last exposure date is defined as the minimum of the last dose date plus 60 days and the last study date.

- Treatment Group 3: last exposure date is defined as the minimum of the last dose date plus 60 days and the last study date.
- Treatment Group 4: last exposure date is defined as the minimum of the last dose date plus 30 days and the last study date.

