6.1.1. US FDA-defined Snapshot Algorithm

The analysis window at Week 54 is defined as from Study Day 323 to Study Day 413, inclusive. All HIV-1 RNA data collected on-treatment (ie, data collected up to 1 day after the last dose date) will be used in the US FDA-defined snapshot algorithm. Virologic outcome will be defined as the following categories:

- HIV-1 RNA < 50 copies/mL: this includes subjects who have the last available on-treatment HIV-1 RNA < 50 copies/mL in the Week 54 analysis window
- HIV-1 RNA \geq 50 copies/mL: this includes subjects
 - Who have the last available on-treatment HIV-1 RNA \geq 50 copies/mL in the Week 54 analysis window, or
 - Who do not have on-treatment HIV-1 RNA data in the Week 54 analysis window and
 - Who discontinue study drug prior to or in the Week 54 analysis window due to lack of efficacy, or
 - Who discontinue study drug prior to or in the Week 54 analysis window due to reasons other than AE, death, or lack of efficacy and have the last available on-treatment HIV-1 RNA \geq 50 copies/mL
- No Virologic Data in the Week 54 analysis window: this includes subjects who do not have on-treatment HIV-1 RNA data in the Week 54 analysis window because of the following:
 - Discontinuation of study drug prior to or in the Week 54 analysis window due to AE or death (regardless of whether the last available on-treatment HIV-1 RNA < 50 copies/mL or not) or,
 - Discontinuation of study drug prior to or in the Week 54 analysis window due to reasons other than AE, death, or lack of efficacy and the last available on-treatment HIV-1 RNA < 50 copies/mL or,
 - Missing data during the window but on study drug.

The flowchart of the US FDA-defined snapshot algorithm is provided in Section 12 ([Appendix 2](#)).

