Kruskal-Wallis test for continuous variable (Y):

```
proc npar1way wilcoxon;
  class trt;
  var Y;
run;
```

9) For race and ethnicity, “Not Permitted”, “Missing”, or “Other” will be excluded from percentage calculation and also excluded for p-value generation for categorical data analysis (eg, CMH test or Kruskal-Wallis test).

10) Study Day 1, Last Dose Date and Last Exposure Date

- a) All the key dates were defined in Section 3.8.1.

11) Study Day 1 and Last Dose Date

- a) All the key dates were defined in Section 3.8.1.
- b) Study Day 1 is defined as the earliest of the dose start dates from any Study Drug Administration eCRF (ie, EX, EX_ARV or EX_IV).
- c) Last Dose Date is defined for subjects who prematurely discontinued study drug according to Study Drug Completion eCRF(ie, SDRGCOMP).
 - i) For subjects who receive SC injection(ie, A subject has data in EX_IV.), the last dose date is defined as the latest nonmissing end date of the study drug used with LEN (ie, the last dose date in EX_ARV).
 - ii) For subjects who do not receive SC injection(ie, A subject has no data in EX_IV.), the last dose date is defined as the earliest of the last dose date of any study drug (ie, the earliest of last dose date in EX or EX_ARV).

- d) Study drug administration: Oral reload will be recorded as an “Unscheduled” visit in the Study Drug Administration eCRF. Subjects with oral reload prior to the 1st dose of SC have “Unscheduled” dosing visits occurred prior to Day 15 visit. Subjects who received a total of 5 tablets of LEN (300 mg) (ie, 2 x 300 mg LEN tablets each for the first 2 days and 1 x 300 mg LEN tablet on the 8th day) prior to “Unscheduled” dosing visits followed by Day 15 visit will be classified as oral reload due to missing scheduled SC dosing. Otherwise, subjects will be classified as oral reload due to missing scheduled oral dosing visit.

12) Adherence to QD Study Drug(s)

- a) Adherence based on 1 study drug(Treatment Groups 1, 2, and 4):

$$\begin{aligned} \text{Adherence (\%)} &= 100 \times \frac{\text{Total No. of pills taken}}{\text{Total No. of pills prescribed}} \\ &= 100 \times \frac{\sum \text{No. of pills taken at each dispensing period for each study drug}^{[1]}}{\sum \text{No. of pills prescribed at each dispensing period for each study drug}^{[2]}} \end{aligned}$$

- b) Adherence based on 2 study drugs(Treatment Group 3):

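### The imputation of a missing or partial last dose date is not capped at discontinuation, so off-drug HIV-1 RNA can count as on-treatment in the Week 54 snapshot

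*SAP*

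**What the plan says.** SAP 3.8.1 defines the last dose date for participants who stopped study drug early, in three bullets.

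- For recipients of an SC injection, it is the latest nonmissing end date of the drug used with LEN.
- For everyone else, it is the earliest of the last dose dates of any study drug.
- The third bullet imputes. It begins "If the date of last dose is incomplete or missing (eg, due to lost to follow-up), the latest nonmissing study drug start dates" and goes on to end dates, clinic visit dates and "the laboratory visit dates excluding the dates of any follow-up visits will be used to impute the last dose date".

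This date controls the primary endpoint. SAP 6.1.1 states: "All HIV-1 RNA data collected on-treatment (ie, data collected up to 1 day after the last dose date) will be used" in the snapshot. It also states: "The analysis window at Week 54 is defined as from Study Day 323 to Study Day 413, inclusive". The last on-treatment value in that window decides the outcome.

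On attendance after stopping, Protocol 6.4.1.1.2 (Groups 1 and 2, after Day 15) asks participants to continue scheduled visits through Week 80 and adds: "If the participant decides to discontinue SC GS-6207 but continues to attend study visits through Week 80, no follow up visits are required". For Groups 3 and 4, Protocol 6.4.1.2 and 6.4.1.3 say of those stopping before Week 64: "If the participant agrees to continue to attend study visits through Week 80, no follow up visits are required". Protocol 6.4.2 schedules the 30-, 90- and 180-Day Follow-up visits from the Early Termination visit.

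**The concern.** The imputation rule appears meant to avoid using dates after treatment ended. The only visits it removes, however, are the named follow-up visits. A stopper who stays in the study has ordinary scheduled visits instead, with plasma HIV-1 RNA drawn at each one (Protocol Appendix 2). For that person the exclusion removes nothing, and the imputed last dose date moves to the latest visit attended.

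Protocol 1.10 says that participants who leave the study will be advised to start alternative therapy, so an off-drug RNA value may reflect another regimen. At stake is whether the Week 54 response rate and the Per-Protocol check describe the assigned regimen.

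**Working it through.** **1. A traced case.** Take a Group 3 participant, so that the SC-specific bullet plays no part. Both drugs stop at about Week 40 and the stop dates are recorded as month and year only. The participant starts other therapy and attends Week 54 on Day 378.

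- The date is incomplete, so the third bullet applies.
- The latest eligible date is Day 378, or later if further scheduled visits follow. The known month is not used.
- The Day 378 RNA is no later than the last dose date plus 1 day, and Day 378 lies in 323 to 413. It is on-treatment.
- If it is < 50 copies/mL, the participant is a success. With a complete stop date there would be no on-treatment RNA in the window, and the outcome would be either ≥ 50 copies/mL or no virologic data. Both are non-successes.

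**2. Direction.** An off-drug rebound would count as ≥ 50. In the FAS this lowers the response rate only if the person also had a true on-treatment value < 50 earlier in the window; otherwise it only moves them from no data to ≥ 50. In the Per-Protocol set it brings in, as a failure, someone who would otherwise usually be excluded.

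**3. Whether anything downstream corrects it.**

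- SAP 6.1.1 consults the discontinuation reason only when the window holds no on-treatment RNA.
- Non-study antiretrovirals are listed and flagged (SAP 7.4.1; Appendix 3 item 16). No rule removes RNA taken after a switch.
- The Per-Protocol set (SAP 3.1.3) uses the same on-treatment term.
- The Appendix 2 footnote ends on-treatment data 1 day after permanent discontinuation. SAP 6.1.1 uses the last dose date. No separate discontinuation date is defined in SAP 3.8.1, so the footnote is not a dependable cap.

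**4. Size per participant.** Denominators are from Protocol 1.2.2.8.

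- LEN groups: 1/52 = 1.9 points; 1/53 = 1.9 points.
- B/F/TAF: 1/25 = 4.0 points.

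**5. Scale against the plan's own figure.** SAP 1.3 gives 39% power with 90.9% response in both groups, a margin of 0.12, and n = 50 and 25. SE = √[0.909 × 0.091 × (1/50 + 1/25)] = 0.0705. Power = Φ(0.12/0.0705 − 1.96) = 0.399, which agrees. Raising the LEN rate by one false success in 50 (2 points), with the control unchanged, gives 0.539.

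**6. Scale against the reported Week 54 results.** Assume k of a LEN group's reported successes are such cases and remove them. The difference from B/F/TAF (23/25) uses the SAP 6.1.2 formula without strata, because stratum counts by group are not given. For Group 1 at k = 0: d = 47/52 − 23/25 = −0.016; p₁* = 47.5/53 = 0.896; p₂* = 23.5/26 = 0.904; SE = √(0.896 × 0.104/51 + 0.904 × 0.096/24) = 0.074.

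| Group | k = 0 | k = 1 | k = 2 |
|---|---|---|---|
| 1 (47/52) | −1.6 (−16.1 to 12.8) | −3.5 (−18.4 to 11.3) | −5.5 (−20.6 to 9.7) |
| 2 (45/53) | −7.1 (−22.5 to 8.3) | −9.0 (−24.7 to 6.7) | −10.9 (−26.8 to 5.1) |
| 3 (44/52) | −7.4 (−22.9 to 8.1) | −9.3 (−25.1 to 6.5) | −11.2 (−27.3 to 4.9) |

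Entries are percentage points (95% CI). The value of k is an assumption, and k = 0 is possible.

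**The case against.** The strongest reply is that the trigger is rare. It needs a missing or partial stop date in someone who still attends in the Week 54 window. Attenders should have an Early Termination visit within 72 hours (Protocol 6.4.1), source records must hold drug start and end dates (Protocol 9.1.6), and queries are resolved or adjudicated before analysis (SAP 2.2). The SAP's own example, loss to follow-up, mostly describes people who no longer attend. The trial is non-confirmatory (SAP 3.5), and one case is small beside intervals of about ±14 to 16 points. All of this stands, and it limits the importance of the point. It does not make the rule correct when it is used.

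It could also be said that follow-up was meant to cover every visit after stopping. The protocol separates the two kinds of visit, so the SAP would have to say so.

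Three stronger readings are tempting, and the documents do not support them.

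- **Fifteen participants affected.** Protocol 1.2.2.8 reports 22 stoppers, 7 of them lost to follow-up, and 22 − 7 = 15. That count covers stops through Week 80 and shows neither missing dates nor continued attendance. It is a loose ceiling, not an estimate.
- **True on-treatment data dropped in Groups 1 and 2.** A reader might infer that the first bullet falls back to the Week 28 F/TAF end date when a later TAF or BIC date is missing. The third bullet covers a missing last dose date, and the SAP does not say which governs. If the fallback did apply to such a person, the imputation would never be reached, so the two errors cannot both occur in one participant. This is an ambiguity and not a demonstrated error.
- **Follow-up visits are only for those who stop attending.** Protocol 6.4.1.1.1 requires the 90-Day visit of pre-Day-15 stoppers who are also asked to attend through Day 15. Protocol 6.4.1.2 and 6.4.1.3 require follow-up visits of Week 64 to 80 stoppers without that condition. Neither exception closes the gap at Week 54.

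**Conclusion.** The point holds as a defect in a stated rule. For a stopper with a partial or missing last dose date who attends in Days 323 to 413, the text counts off-drug RNA as on-treatment in the snapshot and in the Per-Protocol set, and no later step reliably reverses it. This rests on reading follow-up visits as the protocol uses the term and, for SC recipients who have switched partner drug, on the third bullet being reached.

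The number affected is not given and may be zero. Each change in success status is worth about 1.9 points in a LEN group or 4.0 points in B/F/TAF. A reader might infer a bias towards LEN, because stopping was more common there (17/105 SC and 4/52 oral, against 1/25). With no count of affected cases and errors possible in both directions, the documents do not establish a net direction. The rule should be corrected because it governs the primary endpoint and the correction is nearly free. There is no evidence that the reported results are wrong.

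**What to change.** In SAP 3.8.1 and Appendix 3 item 11:

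- Cap the imputed last dose date at the recorded study drug discontinuation date or the Early Termination visit, whichever is earlier and available.
- Keep it within any known month and year, as the SAP already does for partial adverse event and medication dates (7.1.5.2, 7.4.2).
- Exclude every visit after that date, scheduled or follow-up.
- Where neither a discontinuation date nor an Early Termination visit exists, as in loss to follow-up, keep the current rule.
- State that for SC recipients the first bullet uses the end date of the last partner drug dispensed, and that the third bullet applies when that date is missing.

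Align SAP 6.1.1 and the Appendix 2 footnote on the same date.

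Because Protocol 1.2.2.8 already reports Week 54 results, the sponsor can count the affected participants, document any change in the CSR as SAP 1 provides, and carry the corrected rule into the Week 80 analysis. The cost is SAP wording and a few lines of programming, with no new data collection: SAP 4.2.2.2 already relies on a date of premature discontinuation. The downside is that a few stoppers may change snapshot category.

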3.8.2. Analysis Visit Windows

Subject visits might not occur on protocol-specified days. Therefore, for the purpose of analysis, observations will be assigned to analysis windows.

The analysis windows for HIV-1 RNA, CD4+ cell count, CD4 %, Hematology, Chemistry, Lipid Panel, Urinalysis, Urine Chemistry, Urine Pregnancy Laboratory Tests, Vital Signs, and Weight are provided in [Table 3-1](#) and [Table 3-2](#) for the LEN-containing regimen groups (Treatment Groups 1-3) and the B/F/TAF group (Treatment Group 4), respectively.

Table 3-1. Analysis Visit Windows for HIV-1 RNA, CD4+ cell count, CD4 %, Hematology, Chemistry, Lipid Panel, Urinalysis, Urine Chemistry, Urine Pregnancy Laboratory Tests, Vital Signs, and Weight for the LEN-containing Regimen Groups (Treatment Groups 1-3)

Nominal Visit	Nominal Study Day	Visit Window Study Day	
		Lower Limit	Upper Limit
Day 1	1	≤ 1	1
Day 2	2	2	5
Day 8	8	6	11
Day 15	15	12	21
Week 4	28	22	49
Week 10	70	50	91
Week 16	112	92	133
Week 22	154	134	175
Week 28	196	176	231
Week 38	266	232	322
Week 54	378	323	413
Week 64	448	414	504
Week 80	560	505	595
Week 90	630	596	686
Week 106	742	687	777

Table 3-2. Analysis Visit Windows for HIV-1 RNA, CD4+ cell count, CD4 %, Hematology, Chemistry, Lipid Panel, Urinalysis, Urine Chemistry, Urine Pregnancy Laboratory Tests, Vital Signs, and Weight for the B/F/TAF Group (Treatment Group 4)

Nominal Visit	Nominal Study Day	Visit Window Study Day	
		Lower Limit	Upper Limit
Day 1	1	≤ 1	14
Week 4	28	15	49
Week 10	70	50	91
Week 16	112	92	133
Week 22	154	134	175
Week 28	196	176	231
Week 38	266	232	322
Week 54	378	323	413
Week 64	448	414	504
Week 80	560	505	595

3.8.3. Selection of Data in the Event of Multiple Records in an Analysis Visit Window

Depending on the statistical analysis method, single values may be required for each analysis window. For example, change from baseline by visit usually requires a single value, whereas a time-to-event analysis would not require 1 value per analysis window.

If multiple valid, nonmissing measurements exist in an analysis window, records will be chosen based on the following rules if a single value is needed:

- For baseline, the last nonmissing value on or prior to the first dose date of study drug will be selected, unless specified differently. If there are multiple records with the same time or no time recorded on the same day, the baseline value will be the average of the measurements for continuous data (except for HIV-1 RNA, see below), or the measurement with the lowest severity (eg, normal will be selected over abnormal for safety ECG findings) for categorical data.

- For postbaseline values:
 - The record closest to the nominal day for that visit will be selected with the exception of CD4 cell counts and CD4% in which the latest record will be selected and HIV-1 RNA level (see below).
 - If there are 2 records that are equidistant from the nominal day, the later record will be selected.
 - If there is more than 1 record on the selected day, the average will be taken for continuous data (except for HIV-1 RNA, see below) and the worse severity will be taken for categorical data, unless otherwise specified.
- For baseline and postbaseline HIV-1 RNA, the latest (considering both date and time) record(s) in the window will be selected. If both “HIV RNA Taqman 2.0” and “HIV RNA Repeat” (ie, the HIV-1 RNA result obtained from an additional aliquot of the original sample) are available with the same collection time, the results from the “HIV RNA Repeat” will be selected for analysis purposes; otherwise, if there are multiple “HIV RNA Taqman 2.0” records with the same collection time, the geometric mean will be taken for analysis purposes.

